Method and Materials: A total of 24 not well controlled diabetic mellitus (DM) type 2 patients (HbA1c =>7%) with Periodontitis will be recruited. All subjects must have generalized moderate to severe chronic periodontitis. All subjects will be recruited from LLU Health. Subjects will be divided into two group based on their medical needs: HBO therapy and Non HBO therapy. For all subjects demographic data (age, gender, ethnicity, smoking history, alcohol use history, BMI, current medication list) and oral health habits will be obtained. Blood samples for HbA1c determinations, clinical periodontal measurements (plaque index, probing measurements including pocket depth, attachment levels, gingival index and bleeding-on-probing) and subgingival microbial samples will be obtained at baseline and end of the study. Subgingival microbial samples will be collected from three randomly selected sites with probing depth =>5mm and pooled together in a single tube. Both groups will receive full-mouth SRP. The HBOT group will also receive oxygen therapy protocol.

Microbiological Analysis: Collected microbial samples will be processed for DNA extraction and stored at -80°, then sent to the Forsyth Institute (Cambridge, MA) for HOMINGS analysis (The Human Oral Microbe Identification Microarray (HOMIM) technology for detection of about 300 of the most prevalent oral bacterial species, including many that cannot be grown in the laboratory using 16S rRNA gene sequencing).

Statistical analysis: Differences in periodontal clinical outcomes and bacterial profiles from baseline to 12 weeks between non-hyperbaric therapy group and hyperbaric therapy group will be analyzed using the repeated measures ANCOVA (Analysis of Covariance) procedure for paired observations. Periodontal clinical measures at baseline and later time-points will comprise the dependent variables. The ANCOVA procedure will help to account for patient differences in demographics and other clinical factors at baseline while also adjusting for effects of confounding factors.

Hypothesis: “The combination therapy of HBOT and SRP in patients with not well controlled DM type2 and periodontal disease will improve the periodontal clinical parameters and reduce subgingival microbial load.”

Time line and Milestones:

We anticipate a period of one year to complete the proposed research.

Protocol Submission and Approval: September 2015

Preparations, team training and calibration: 10/1/15-10/30/15

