A total of 24 not well controlled type 2 diabetic subjects with Periodontitis presenting for medical care at LLU Health will be recruited for the study (see power analysis under statistical section). An additional 6 subjects will also be recruited to compensate for subject attrition. Subjects will be divided into two group based on their medical needs: HBO therapy and Non HBO therapy. For all subjects demographic data (age, gender, ethnicity, smoking history, alcohol use history, BMI, current medication list) and oral health habits will be obtained. HBOT subjects will be recruited first and control subjects (non HBO group) will be recruited after to match the HBO subjects on all parameters including HbA1c level to minimize bias.

Inclusion Criteria:

Diabetic patients must meet the following inclusion criteria:

1. An established diagnosis of DM type 2 (HbA1c =>7%).
2. Subjects must have a minimum of 10 permanent teeth.
3. Age range 35 year or older.
4. All subjects must be registered patients at LLU Health.

Exclusion Criteria:

Individuals with the following conditions may NOT participate in the study:

1. Well-controlled type 2 diabetics (HbA1c <7%) and type 1 diabetic patients.
2. Other systemic conditions with known association with periodontitis, e.g. AIDS, Down's syndrome, current smoker, head and neck radiation, Xerostomia, currently under chemotherapy.
3. Intra-oral conditions present which might interfere with accuracy of periodontal probing, e.g. gingival overgrowth, orthodontic wires, excessive calculus.
4. Not a registered patient at LLU Health.
5. Overweight/obese individuals (BMI greater than 45 %)
6. Pregnancy or lactation

[figure not shown]
QUESTIONNAIRE:

Oral Health Interview: subjects will be interviewed regarding personal and professional dental care habits and cigarette smoking habits.

Study Plan:

Group	Not eligible for HBOT N=15	Eligible for HBOT N=15
Medical History Review Medical Assessments	Yes	Yes
Baseline HbA1c	Yes	Yes
Baseline Periodontal Evaluations	Yes	Yes
SRP	Yes	Yes
HBO Therapy	No	Yes (20-40 daily treatments for 8 weeks)
Final Periodontal Evaluation (12 weeks after SRP)	Yes	Yes
Final HbA1c (12 weeks after SRP)	Yes	Yes

Note: subjects in both groups will be receiving any needed medical care

CLINICAL EVALUATIONS

Medical Assessments:

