Determination of diabetes status: review of medical history and Hemoglobin A1C testing will be done under the direction of [name] or qualified residents. All subjects entered in the study will go through a comprehensive medical evaluations and blood testing to determine the diabetic status.

Dental/Periodontal Examination:

[name] will direct and supervise all dental/periodontal examinations. The dental examiners will be blinded to HBOT therapy status. At initial examination and 4 weeks after HBOT, all subjects will undergo comprehensive oral evaluations followed by recoding of the Loe 1967 gingival index (GI), periodontal probing measurements (PPD), bleeding on probing (BOP), clinical attachment loss (CAL), and Quigley & Hein plaque index (PI). Average scores will be computed for each measure per subject.

Periodontal Probing Measurements:

All fully erupted teeth present, excluding third molars, will be measured. A pressure controlled periodontal probe (Williams Probe, with 1mm marking, Hu-Friedy) will be used to determine probing depth at six sites per tooth: mesiobuccal, buccal, distobuccal, mesiolingual, lingual, distolingual. The position of the gingival margin in relation to the cementoenamel junction will also be recorded at the same 6 sites per tooth to the nearest mm. A negative sign will be given

when the gingival margin is coronal to the cementoenamel junction and a positive sign will be given when it is apical. Clinical attachment level (CAL) will be calculated by adding probing depth to position of gingival margin. Percentage of teeth with at least one site having loss of attachment (CAL) ≥ 5 mm will be calculated for each subject. Also, the presence or absence of gingival redness, suppuration, bleeding on probing (BOP), and supragingival plaque accumulation will be recorded. Clinical measurements will be taken at baseline and at 3 months post-therapy.

Periodontitis diagnosis:

Periodontal diagnosis will be based on the 1999 AAP Classification of Periodontal Diseases. Diabetic individuals with Chronic Periodontitis will be recruited for the study. Selected subjects must have 5% or higher of scored teeth with attachment loss ≥ 5 mm and probing depth ≥ 5 mm.

Treatment Protocol:

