Subjects in both treatment groups will receive full-mouth scaling and root planing (SRP) under local anesthetic, and instruction in proper homecare procedures at Prince Hall School of Dentistry at LLU. Five dental student investigators will provide full-mouth SRP. Wound care management will be provided to all subjects at LLUHealth. The hyperbaric treatment group will also receive their oxygen therapy protocol as planned in the medical center. Each session of HBOT would be given in LLU Health Hyperbaric Treatment Center per order of hyperbaric clinician.

Calibrations:

[name] (as mentioned in page2) is sole examiner and assessor of all steps, and would be blinded regarding the status of the patients. [name] is an experienced examiner who has been repeatedly calibrated in performing the measures described above. Before data collection begins and periodically throughout the study period, [name] calibrates the dental examiners to insure reliability of clinical measurements, and prevent bias introduced by “examiner drift”.

Sample Collection

Blood Sampling:

Blood will be collected by a single venipuncture. The initial blood sample will be collected at the baseline appointment and the final blood sample will be collected at the last appointment (3 months after completing SRP).

Microbiological Sampling:

Microbial samples will be collected by same examiner at baseline and 3 months after SRP. Samples will be taken from the same sites at all visits. Subgingival samples will be collected from 3 randomly selected sites with probing depth ≥ 5 mm. The sample sites will be isolated with cotton rolls and air-dried. Supragingival plaque will be removed with sterile cotton pellets and scalers. Subgingival plaque samples will be taken separately from each site using sterile Gracey curettes. All three samples will be pooled in 1.5-mL tube containing 50 mL TE (50 mM Tris-HCl and 1 mM EDTA [pH7.6]) (Khocht et al., 2012).

Microbiological Analysis:

Collected microbial samples will be processed for DNA extraction and stored at Loma Linda University in the research laboratory of [name], then sent to [name] (HOMINGS) at the Forsyth Institute ([name]). A total of 300 of the most prevalent oral bacterial species, including many that cannot be grown in the laboratory will be assessed by [name] (Forsyth Institute, Boston, MA).

The following technique will be used:

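### HBOT subjects are recruited first and controls after: read as two blocks, enrolment period coincides with group, so changes over time in treatment response are largely inseparable from HBOT and the examiner's blind is not secure

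*Combined protocol and SAP*

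**What the plan says.** Groups are set by medical need, not by chance. Under Subject Characteristics the combined protocol and SAP states: "HBOT subjects will be recruited first and control subjects (non HBO group) will be recruited after to match the HBO subjects on all parameters". The matching variables named there extend to HbA1c, and the stated aim is to reduce bias. No overlap or interleaving of the two groups is described.

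The Dental/Periodontal Examination section states that "The dental examiners will be blinded to HBOT therapy status". Calibrations adds that one person "is sole examiner and assessor of all steps, and would be blinded regarding the status of the patients", although the same paragraph also refers to examiners in the plural. The visible text gives no procedure for hiding group or recruitment order. Calibration is repeated during the study to limit examiner drift. Under Treatment Protocol, "Five dental student investigators will provide full-mouth SRP". The timeline allows a month beforehand: "Preparations, team training and calibration: 10/1/15-10/30/15".

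The ANCOVA adjusts for baseline demographics, clinical factors and confounders in general. It does not name calendar time or enrolment order.

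The later examination is timed in more than one way. Dental/Periodontal Examination says "At initial examination and 4 weeks after HBOT, all subjects will undergo comprehensive oral evaluations". Periodontal Probing Measurements puts it 3 months after therapy. The Study Plan table puts it 12 weeks after SRP, and Microbiological Sampling says "Microbial samples will be collected by same examiner at baseline and 3 months after SRP".

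**The concern.** In a non-randomised comparison, matching and blinded examination are the main protections. Two-block recruitment weakens both in ways that matching on patient characteristics cannot repair.

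- **Time effects on response.** If SRP quality, wound care or medication practice changes between the first and second block, that change falls almost wholly on one group and is read as an HBOT effect, or hides one.
- **Blinding.** A single examiner who knows the recruitment order could tell from the date and type of visit which group a subject belongs to. Probing depth, gingival index and bleeding all involve some judgement.

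The pilot is meant to supply preliminary data for a larger funded study, so a contaminated estimate would carry forward.

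**Working it through.** **Plan's own figure.** Power Analysis gives 12 per group for 80% power, 2 mm difference, SD 1 mm, alpha 0.05. This does not reproduce. With a two-sided t test, 6 per group suffice (power 87.6%), and 12 per group give 99.7%. That is a separate matter. Below, the plan's inputs (12 per group, SD 1 mm) are used on one basis: two-sided 0.05, 80% power, noncentral t.

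**Calendar.** Time line and Milestones gives 1 November 2015 to 30 May 2016 for recruitment, treatment and follow-up: 211 days = 30.14 weeks. Less 12 weeks of follow-up, 30.14 − 12 = 18.14 weeks remain for enrolment. Two equal blocks last 18.14 / 2 = 9.07 weeks each. Even recruitment, and SRP at the baseline visit, are assumptions.

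**Two blocks.** The correlation of enrolment order with group is r = 0.867 (12 per group), so r² = 0.751.

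- Variance inflation = 1/(1 − r²) = 1/(1 − 0.7513) = 4.02.
- SE of the group difference = √(2/12 × VIF) × 1 mm: 0.408 mm unadjusted, 0.819 mm with a linear order term.
- Detectable difference is about 2.93 to 2.94 SE: 1.20 mm unadjusted (22 df), 2.41 mm adjusted (21 df).
- Power for 2 mm falls from 99.7% to 64%.
- With 15 per group, the detectable difference goes from 1.06 to 2.13 mm.

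**What dates reveal, if the examiner knows when recruitment switched.** HBOT final visits fall in weeks 12 to 21.07 and control baselines in weeks 9.07 to 18.14. They overlap for 18.14 − 12 = 6.14 weeks. With 15 + 15 subjects, 6.14/9.07 × 30 = 20.3 visits are ambiguous on date alone, so about 40 of 60 are identified. Visit type settles the rest.

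**What passes into the HBOT estimate.** Simulation with 12 per group, no HBOT effect, SD 1 mm and baseline-to-final correlation 0.5 (assumed), 4000 runs. All sizes of time effect are assumptions; the documents give none.

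- Linear additive measurement drift: bias about 0 in change scores and type I error about 5%. In baseline-adjusted ANCOVA, a total drift of 1 mm leaves about 0.15 mm.
- A difference between blocks in treatment response passes through almost in full. For 0.25, 0.5 and 1.0 mm the false-positive rates are about 10%, 22–27% and 65–75% (change score to ANCOVA).
- A gradual change in response over the enrolment period passes about half its total. For 1.0 mm the false-positive rate is 21–25%.

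**Rolling matched enrolment.** Let HBOT starts be uniform over L = 18.14 − w weeks, with each control following within w weeks of its match.

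- Lags spread evenly over 0 to w: r² = (w/4)² / (L²/12 + w²/24 + (w/4)²). For w = 4: 1/(16.67 + 0.67 + 1) = 0.055.
- All lags at w: r² = (w/2)² / (L²/12 + (w/2)²). For w = 4: 4/(16.67 + 4) = 0.194.

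| Window | VIF, lags even | VIF, lags at limit | Detectable difference, 12 per group |
|---|---|---|---|
| 4 weeks | 1.06 | 1.24 | 1.23 to 1.34 mm |
| 6 weeks | 1.16 | 1.73 | 1.29 to 1.58 mm |
| 8 weeks | 1.36 | 2.87 | 1.40 to 2.03 mm |
| Two blocks | 4.02 | – | 2.41 mm |

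**Examination timing.** The Study Plan gives 20 to 40 HBOT sessions over 8 weeks. If HBOT starts at SRP (not stated) and lasts 8 weeks, 8 + 4 = 12 weeks and the schedules agree. They separate if the course is shorter or starts later. For controls, a time counted from HBOT is undefined.

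**The case against.** The strongest reply has five parts.

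1. *The sentence does not require all HBOT subjects to enrol before any control.* True. If the sponsor meant rolling enrolment, exposure is at the lower levels in the table and only the wording needs changing. As written, a team following it literally would recruit in blocks.
2. *Time effects largely cancel or are controlled.* This stands for measurement. Constant offsets and steady drift cancel in change from baseline, calibration is periodic, the probe is pressure-controlled, and the microbial assay is read at an outside institute. It does not stand for changes in response to treatment. A practice effect among the student operators is hypothetical, however, and the training month reduces it.
3. *The plan includes no enrolment-order term.* Correct. A reader might infer that the planned analysis can detect only 2.4 mm. The documents do not support that: the figure is the price of a later correction, not a property of the planned ANCOVA.
4. *The blind is not shown to be broken.* Also correct. Nothing says that the examiner knows the order, and front matter that introduces the examiner is not in the available text. A reader might infer that unblinding is established; the documents support only that the blind is not secure.
5. *Recruiting HBOT subjects first helps matching.* It does, and closer calendar balance costs some closeness of match. In a budget-limited pilot this is a judgement, but the trade-off can be made at low cost.

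The timing wording might also be taken to reveal group by itself. It does not: the schedules nominally coincide at 12 weeks. The remaining fault is a reference point that controls lack and that can move with the HBOT course.

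**Conclusion.** The point holds as a design weakness worth correcting, conditional on the two-block reading. On that reading about 75% of the variance in enrolment order is shared with group. A change over time in treatment response would be largely inseparable from HBOT, and blinding would depend on the examiner not knowing the recruitment order. The size and direction of any bias are unknown. The false-positive rates above show only what assumed effects would do.

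The variance inflation of 4.0 and the rise from 1.2 to 2.4 mm illustrate why later adjustment is a poor rescue. They rest on even recruitment in the stated calendar, 12 per group, SD 1 mm and a linear term. Rolling enrolment removes most of this cost at a 4-week window under either lag assumption. At 8 weeks the benefit depends on how lags fall, and if all lie at the limit the 2 mm target is again just missed (2.03 mm).

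**What to change.** Replace the recruitment sentence under Subject Characteristics with wording such as: *Each control will be enrolled as soon as possible after the HBOT subject it matches, with a target of 4 weeks; a longer interval is an exception and its reason is recorded.*

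In addition:

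- Spread each SRP operator across both groups.
- Keep recruitment order and pairing from the examiner, for example with neutral subject IDs and examination sessions shared by both groups.
- Record operator and visit date for each subject, for a sensitivity analysis.
- Reconcile the statements on the later examination in Dental/Periodontal Examination, Periodontal Probing Measurements, Study Plan and Microbiological Sampling, so that both groups are examined on one schedule defined for every subject.

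The cost is wording and scheduling, with no extra visits or staff. The downside is a smaller pool of candidates at any one time: about 4 weeks of eligible patients per HBOT subject, against about 9 weeks shared by all 15 in a later block. Matching may be somewhat less close, with the planned ANCOVA adjusting for what remains. In partial return, HBOT recruitment has 18.14 − 4 = 14.14 weeks instead of 9.07, so the rate needed falls from 15/9.07 = 1.65 to 15/14.14 = 1.06 subjects per week.

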In summary: DM is a growing chronic health problem in the United States and the world. It is a well-established risk factor for periodontal disease. Periodontitis in turn can increase insulin resistance and potentially aggravates diabetes. Managing periodontitis in diabetics is important. However, poorly controlled diabetics do not respond favorably to periodontal therapy. HBOT as an adjunctive therapy, along with SRP, has promise to improve the outcomes of non-surgical periodontal therapy and reduce subgingival microbial load in poorly controlled diabetics. It may also have greater impact on the subgingival microbial profile than SRP alone. The main objectives of the research are investigating the combined effect of both therapies vs. the effect of SRP alone on the periodontal clinical outcome as well as the subgingival microbial profile in poorly controlled diabetics.

Hypothesis: “The combination therapy of HBOT and SRP in patients with not well controlled DM and periodontal disease will improve the periodontal clinical parameters and subgingival microbial profiles due to HBOT immediate and delayed effects on neovascularization, growth factors, osteogenesis, PMN’s killing function, and oxygen saturation in anaerobic bacterial cytoplasm.”

Alternative hypothesis: Combination therapy of HBOT and SRP in patients with poorly controlled DM and periodontal disease will not have a significant improvement on the periodontal clinical parameters and subgingival microbial profiles.

RESEARCH DESIGN AND METHODS

The Approach:

Study Design: The proposed pilot study is a longitudinal observational study to compare periodontal treatment (SRP) outcome between 2 diabetic patient groups receiving medical care at LLUMC either with or without adjunctive Hyperbaric Oxygen Therapy. The results will provide essential preliminary data to plan for an R21 NIH study that will be powered to comprehensively assess treatment outcomes and better understand the mechanisms involved.

Subject Characteristics:

All subjects will be recruited from the diabetic patient pool at LLU Health. Drs. [name] and [name] at their respective institutions will work together to identify and refer prospective subjects to the study. All subjects must have not well controlled DM type 2 (as defined below). In addition, all subjects must have generalized moderate to severe chronic periodontitis (as defined below).

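### The stated 80% power does not follow from the power inputs (12 per group gives 91% to 99.7%), and the numeric entry rule does not guarantee the three deep sites that the microbial sample needs

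*Combined protocol and SAP*

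**What the plan says.** **Power.** The Power Analysis section takes a 2 mm difference between groups in average pocket depth, SD 1 mm and alpha 0.05, and concludes that 80% power requires 12 subjects per group. It does not say whether the SD is that of the 12-week value or of the change, or whether the test is two-sided. Subject Characteristics adds 6 subjects for attrition, and the Study Plan table shows 15 per group. The analysis for Aim 1 is a repeated measures ANCOVA of pocket depth from baseline to 12 weeks.

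**Entry and sampling.** Method and Materials in the Abstract states: "All subjects must have generalized moderate to severe chronic periodontitis". Subject Characteristics repeats this: "all subjects must have generalized moderate to severe chronic periodontitis (as defined below". The Inclusion Criteria section opens with "Diabetic patients must meet the following inclusion criteria" and lists four items (diabetes diagnosis, number of teeth, age, registration at the institution), none of them periodontal. The definition comes later, under Periodontitis diagnosis: "Periodontal diagnosis will be based on the 1999 AAP Classification of Periodontal Diseases". That section then refers simply to chronic periodontitis and gives one numeric rule: "Selected subjects must have 5% or higher of scored teeth with attachment loss ≥ 5 mm and probing depth ≥ 5 mm". Under Periodontal Probing Measurements, a tooth counts for attachment loss on a single site: "Percentage of teeth with at least one site having loss of attachment (CAL) ≥ 5 mm will be calculated for each subject". For Aim 2, the Abstract says: "Subgingival microbial samples will be collected from three randomly selected sites with probing depth =>5mm and pooled together in a single tube". Microbiological Sampling repeats the three-site requirement and has the same sites sampled again at 3 months.

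**The concern.** The power statement is the only quantitative justification of the sample size. A standardised difference of 2 is very large, and 12 per group looks far too many for only 80% power. If the chain from inputs to sample size is broken, nobody can tell which input was really used or what difference the study can detect. The protocol presents the pilot as preparation for a fully powered trial, so an untraceable power basis could be carried forward.

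The entry rule raises a separate question of feasibility. Aim 2 analyses bacterial counts at baseline and follow-up from a pooled sample of three deep sites. If a subject can satisfy the numeric rule with fewer than three such sites, the planned sample cannot be taken, and the plan does not say what happens then.

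**Working it through.** **A. Power statement**

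Inputs, all from Power Analysis: difference Δ = 2 mm, SD = 1 mm, alpha = 0.05, power = 80%, equal groups. Sidedness and the meaning of the SD are not stated, so alternatives are tried. The test is an unadjusted two-sample comparison of subject-level means; covariate adjustment is not modelled, because the documents give no baseline correlation.

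*Attempt to reproduce 12 per group.* Normal approximation: n = 2·SD²·(z₀.₉₇₅ + z₀.₈₀)²/Δ² = 2 × 1 × (1.960 + 0.842)²/4 = 3.92, so 4 per group. The t-test has noncentrality (Δ/SD)·√(n/2) on 2n − 2 degrees of freedom. It gives 79.1% at n = 5 and 87.6% at n = 6, so 6 per group. The stated 12 is not reproduced.

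*Power at 12 per group, SD applying to the compared quantity.* Noncentrality 2 × √6 = 4.90, 22 degrees of freedom, critical value 2.074: power 99.7% (99.9% if one-sided).

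*Power at 12 per group, SD applying to each visit and the change compared.* SD of change = SD·√(2(1 − ρ)). With uncorrelated visits (ρ = 0) this is 1.41 mm. Noncentrality (2/1.41) × √6 = 3.46: power 91.1%. For 80%, 8 per group gives 74.9% and 9 gives 80.4%, so 9 per group. At ρ = 0.5 the SD of change is again 1 mm and the first case returns. Any positive correlation therefore puts power above 91.1%.

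*Other variants (per group, t-test unless noted; SD 1 mm):*

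| Variant | n per group |
|---|---|
| One-sided 0.05, 80% power | 4 |
| Two-sided 0.05, 90% power | 7 |
| Two-sided 0.01, 80% power | 8 |
| Wilcoxon, efficiency 0.864: 6/0.864 = 6.9 | 7 |
| Two-sided 0.05, 99% power | 11 |

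Only 99% power comes near 12, and that contradicts the stated 80%. The total sample size under the two-sided t-test is 2 × 6 = 12, so a total may have been read as a per-group number. The documents do not show this.

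*What 12 per group does correspond to at 80% power.* The detectable standardised difference is 1.197: about 1.20 mm at SD 1 mm, or 1.197 × 1.41 = 1.69 mm if the SD of change is 1.41 mm. For a 2 mm difference, the SD would have to be 2/1.197 = 1.67 mm.

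*Attrition.* 24/(1 − 0.20) = 30, so the 6 extra subjects are consistent with 20% attrition.

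**B. Entry rule against sampling need**

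Inputs: the 5% threshold (Periodontitis diagnosis); third molars excluded, so at most 28 scored teeth, with six sites each (Periodontal Probing Measurements); three sites with probing depth of 5 mm or more (Abstract and Microbiological Sampling).

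Minimum qualifying teeth = 0.05 × scored teeth, rounded up:

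| Scored teeth | 5% of teeth | Teeth needed |
|---|---|---|
| 10 | 0.50 | 1 |
| 20 | 1.00 | 1 |
| 21 | 1.05 | 2 |
| 28 | 1.40 | 2 |

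If one site is enough for a tooth to qualify, the numeric rule guarantees one site of 5 mm or more (up to 20 scored teeth) or two (21 to 28), against three needed. The one-site convention is explicit only for attachment loss; the entry sentence does not say how many sites per tooth count for probing depth.

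**The case against.** On power, the mismatch is on the safe side. Under either reading of the SD, 12 per group exceeds what 2 mm requires, and the study is a budget-limited pilot. That stands: a reader might infer that the sample size is wrong or that the study is underpowered for its stated target, and the documents support neither. A single corrected figure of 99.7% would also be unsafe while the SD is undefined, which is why both cases are given. A further allowance for covariate adjustment might have been intended, but the plan states none.

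On entry, the required diagnosis is worded as mandatory in two places, and a published classification is named. The natural reading is that the 5% rule adds to that diagnosis. A subject with widespread moderate to severe disease would usually have three deep sites. This also stands, and it keeps the gap conditional. Three stronger readings are tempting:

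- *That the plan has no periodontal entry cut-off.* It has a numeric one and a named classification. What is missing is a stated link between the 5% rule and the terms for extent and severity. The classification's own thresholds are not reproduced and cannot be checked from the documents.
- *That severity standards could drift between groups,* because "HBOT subjects will be recruited first and control subjects (non HBO group) will be recruited after". The Calibrations section describes a sole, blinded, experienced examiner with repeated calibration against drift; the examination section also blinds examiners to HBOT status; and controls are to be matched to HBOT subjects. The documents do not support this harm.
- *That Aim 2 would lose a material share of subjects.* The documents give no basis for any share, and 15 rather than 12 per group are to be recruited.

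What remains is that no rule covers a subject with fewer than three sites.

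**Conclusion.** The power statement is wrong as written. For a 2 mm difference, 12 per group gives between 91.1% (per-visit SD, uncorrelated visits) and 99.7% (SD of the compared quantity), not 80%. These figures assume a two-sided unadjusted t-test with equal SDs; a one-sided test would only widen the gap. The consequence is an untraceable justification, not a shortage of subjects.

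The entry point is secondary, a cheap improvement. Taken alone, and if one site qualifies a tooth, the numeric rule falls one or two sites short of what the microbial sample needs. How many enrolled subjects would be affected cannot be derived from the documents. If the full diagnosis is enforced, it is probably few.

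**What to change.** **Power Analysis.** Keep the sample size. Say whether the SD of 1 mm is for the 12-week value or for the change, and whether the test is two-sided. Then restate either the power or the detectable difference. For example, if the SD applies to the compared quantity: *with 12 subjects per group and a two-sided alpha of 0.05, the study has 80% power for a difference of about 1.2 mm and 99.7% power for 2 mm, assuming SD 1 mm.* If the 80% and the 2 mm were both intended, the SD behind them would be about 1.67 mm and should be stated as such. This is a change of wording only.

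**Inclusion Criteria.** Add: *at least three sites with probing depth of 5 mm or more at baseline.* Reconcile the Abstract, Subject Characteristics, Inclusion Criteria and Periodontitis diagnosis by stating how the 5% rule relates to the required generalized moderate to severe diagnosis, and whether one site is enough for a tooth to count for probing depth. The cost is one extra count at screening, from probing data already recorded, and possibly a rare additional exclusion.
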